8.9.4. MTAP testing

A requirement for inclusion in the study is the availability of archival tumor tissue, or willingness to undergo a fresh biopsy to determine MTAP status.

In part 1, MTAP testing will be performed retrospectively.

In Part 2, prospective MTAP testing is required to confirm MTAP deficiency for enrolment unless local MTAP or *CDKN2A* results are available. In this latter situation, central MTAP testing will be used to confirm MTAP deficiency.

Additionally, SDMA IHC may be conducted to correlate MTAP expression level and SDMA level with response.

Screen failure tissue, used for central testing will be retained. This tissue may be used in the validation of potential diagnostic assays to detect MTAP.

8.9.5. Coagulation markers

Markers of hemostasis will be assessed and monitored over time to better understand the potential mechanism leading to venous thromboembolic (VTE) events. Analytes of interest may include, but not limited to, D-dimer, fibrinogen, soluble P-selectin and several factors from the extrinsic and intrinsic coagulation pathways, such as factors II, V, VII, VIII, IX, X, XI and XI and von Willebrand Factor..

8.10. Patient Reported Outcomes (PRO)

8.10.1. Qualitative Telephone Interviews

To further evaluate disease and intervention related symptoms and associated impacts on function and health-related quality of life, participants in Part 2 only, will participate in a qualitative interview conducted via telephone. The interview will be conducted by a trained interviewer in the participant's native language and will be audio recorded for transcription and analysis.

The telephone interview is to be completed within 21 days following completion of the week 8 disease assessment and following the intervention discontinuation visit in Part 2 of the study. Participants who have the intervention discontinuation visit (TDV) within 30 days of the week 8 interview are not required to repeat the interview.

9. STATISTICAL CONSIDERATIONS

9.1. Hypotheses

9.1.1. Dose Escalation

With respect to the primary objectives and endpoints, no specific statistical hypotheses are being tested in Part 1. The primary focus will be on determining the RP2D for further exploration, based upon the safety, PK, food effect on PK and efficacy profiles of GSK3368715.

9.1.2. Dose Expansion

The primary goal of Part 2 is to evaluate clinical activity in each disease specific cohort for GSK3368715 for MTAP- subgroup and MTAP+ subgroup separately.

All evaluations in Part 2 are designed to exclude a 10% response rate representing best available therapy in favour of a 30% response rate.

9.2. Sample Size Determination

The sample size for each part of the trial was chosen to adequately characterize the safety, clinical activity, PK, and pharmacodynamic marker data based on the objectives of each part of the study.

Part 1 will enroll approximately 60 participants. Dose escalation and de-escalation decisions will be guided by an N-CRM model. In Part 1 where an N-CRM design is utilized it is assumed that approximately 50 participants will complete the DLT evaluation period. Approximately 10 participants will be enrolled at a dose or doses near the MTD/RP2D in each PK/PD/Biomarker cohort. At least twelve (12) participants will be enrolled in the food effect sub cohort as per the minimum sample size recommendation from FDA food effect guidance. For both C_{max} and AUC_{last}, a total sample size of 12 patients achieves 80% power at a 10% significance level when the actual ratio of the means in the presence or absence of food is 1.0, if the coefficient of variation (COV) on the original, unlogged scale is 0.206, and the equivalence limits of the mean ratio are 0.80 and 1.25; if the COV on the original, unlogged scale is 0.334, the equivalence limits of the mean ratio will be 0.70 and 1.428 to achieve the same level of power.

In Part 2, a maximum of 36 participants will be enrolled in the DLBCL cohort and up to 35 participants will be enrolled in each of the solid tumor cohorts. If all cohorts enroll the maximum number of participants, this will result in 141 participants in total.

Additional tumor-specific cohort(s) and combinations may be added by protocol amendment, based upon emerging pre-clinical data, or clinical data from the dose-escalation portion of the study.

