1. The assessments required at the treatment discontinuation visit (TDV) must be completed within 30 days from the date that study intervention was discontinued and must occur prior to the start of subsequent anti-cancer therapy; the window for this visit is +10 days

Table 4 Schedule of Activities (SoA) (Food effect cohort)

Food effect cohort (Section 4.1.1.1); samples collected in this section are in addition to any samples, studies, and visits described in Table 2) ³									
	D1	D2	D3	D4	D5 ⁴	D6	D7	D8	D9 and beyond
Administer study drug ¹	X				X				←-----daily dosing----->
Plasma PK samples ²	X	X	X	X	X	X	X	X	X ³

1. Study drug should be administered in fed or fasted state, based on assignment as described in Section 4.1.1.1
2. PK samples on Days 1 and 4/5 should be collected at 0 (pre-dose), 0.25h ± 5 min, 0.5h ± 5 min, 1h ± 5 min, 1.5h ± 5 min, 2h ± 10 min, 3h ± 10 min, 4h ± 10min, 6h ± 30 min, 8h ± 30 min, 12h ± 2h, 24± 2h, 48± 2h and 72± 2h hours post dose
3. Refer to Table 2 for subsequent PK sample requirements
4. In order to accommodate clinic schedules, the Day 5 dosing (including all PK assessments) may be performed one day earlier (on Day 4), i.e. Days 5 to 8 would shift to Days 4 to Day 7, and then all subsequent PK assessments from then on would follow the same schedule as in Table 2

NOTE: Participants in the food effect sub-study are subject to all screening, safety, PK, and efficacy evaluations detailed in Table 1 and Table 2. Samples collected in this section are in addition to any samples collected in Table 2, with the exception of Day 1-8 PK collections, in which the time points in Table 4 supersede those in Table 2

[figure not shown]
Any participant who experiences vomiting at or between 0.25-3 h will be removed from statistical analysis of PK comparability between fasted/fed state

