4.1.1.1. Food effect Cohort

Once a RP2D is identified, a food effect sub-study may be initiated. It will be an open-label, randomized, single dose, two period, cross over study to investigate the effect of a high-fat, high-calorie meal on the bioavailability of GSK3368715 with a tablet formulation at or near the RP2D. Initiation or completion of this sub-study is not required prior to initiating part 2. GSK3368715 dosing (fed then fasted, or fasted then fed) will be separated by at least 3days. A minimum of 12 participants in the United States may be enrolled in the sub-study. A participant requiring dose reduction or discontinuation from study before completion of at least 48 hours after dosing in fasted/fed state in the sub-cohort will be replaced by a new participant. All participants enrolled to the sub-study, on completion of their participation in this segment of the study, will continue on a daily dosing schedule until discontinuation criteria are met, as described in Section 7.1.

The food effect sub-study will be open to participants with histologically- or cytologically confirmed solid malignancies as described for Part 1 in Section 5.1.

The high-fat (approximately 50% of the total caloric content of the meal), high-calorie meal (approximately 800 to 1000 calories) will be the representative example given by the 2002 US Food and Drug Administration (FDA) guidance [FDA, 2002]. Additional details of the required meal will be provided in the SRM.

Participants enrolled in the sub-study will be assigned to one of two sequences, as described in [Table 5](#); equal numbers will be assigned to each sequence. The schedule of visits for participants enrolled in the sub-study is detailed in [Table 4](#) in Section 1.3. Upon completion of the sub-study, all participants will continue to undergo scheduled assessments as described in [Table 2](#). Additional details, including the process of sequence assignment, will be provided in the SRM.

Table 5 Food Effect Sub-Study

Food effect cohort (single dose administrations)			
Sample size	Sequence	Period 1 (W1D1)	Period 2 (W1D4/D5)
6	1	Fasted	Fed
6	2	Fed	Fasted

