9.6.3.2.1. Food Effect Sub-Study

Pharmacokinetic (PK) parameters AUC(0-∞), AUC(0-t) and Cmax will be log-transformed and analyzed separately using a mixed-effects model with fixed-effect term for fed status (fed or fasted), and participant as a random effect. Point estimates and their associated 90% CIs will be constructed for the differences between fed and in fasted state. The point estimates and their associated 90% CIs will be then back transformed to provide point estimates and 90% CIs for the ratios of fed/fasted. Non-parametric methods such as the

Hodges and Lehmann estimator will be used to estimate the median differences between the fed treatments and the fasted state treatments for t_{max} and $t_{1/2}$. An associated 90% CI for the median differences will be constructed.

Based on the US FDA guidance on food-effect bioavailability studies, the absence of a food-effect will be established if the 90% CI of the ratio for C_{max} and AUC, based on log-transformed data, is within the 80 to 125% equivalence limit. Recommendation on the clinical significance of the effect of food will be based on the magnitude of the change and our understanding of the exposure-clinical response relationship. For the evaluation of food effect, t_{max} at fed and fasted status will be presented by participant and dose cohort in tabular and graphical form.

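### The 80% power stated for the 12-participant food-effect comparison fits an 80% confidence interval; under the protocol's own 90% CI rule it is about 61%

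*Protocol*

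**What the plan says.** Protocol 9.2 gives two grounds for the size of the food-effect cohort. The first is regulatory: at least twelve participants, "as per the minimum sample size recommendation from FDA food effect guidance". The second is a power statement for Cmax and AUC: "a total sample size of 12 patients achieves 80% power at a 10% significance level when the actual ratio of the means" is 1.0. It is given for two scenarios: a CV of 0.206 with limits 0.80 to 1.25, and a CV of 0.334, for which "the equivalence limits of the mean ratio will be 0.70 and 1.428 to achieve the same level of power". The section does not say whether 10% is the level of each one-sided test or the overall level. Nor does it say whether the CV is within-participant or total.

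The decision rule is in Protocol 9.6.3.2.1: "the absence of a food-effect will be established if the 90% CI of the ratio for" Cmax and AUC "is within the 80 to 125% equivalence limit". The model there has fed status as a fixed effect and participant as a random effect. Section 4.1.1.1 describes a randomised two-period crossover with six participants per sequence, and also treats the number as a floor: "A minimum of 12 participants in the United States may be enrolled in the sub-study".

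**The concern.** A 90% confidence interval lying inside the limits is the same as two one-sided tests at 5% each. A power figure worked out at 10% per test describes a looser criterion, an 80% interval inside the limits. If that is how the 80% was obtained, it is not the power of the rule that 9.6.3.2.1 would apply, and a reader of 9.2 would overrate the chance that 12 participants can show absence of a food effect. Section 4.2 says this cohort's data may be used to change dosing instructions in this and later studies, so the chance of a conclusive answer should be stated correctly.

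A second mismatch is that the limits 0.70 to 1.428 in the other scenario appear nowhere in the decision rule.

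**Working it through.** **Inputs.** From 9.2: n = 12, true ratio 1.0, CV 0.206 with limits 0.80 to 1.25, and CV 0.334 with limits 0.70 to 1.428. From 4.1.1.1: two-period crossover, equal sequences. From 9.6.3.2.1: 90% CI, limits 80 to 125%. Assumed: the CV is within-participant, and all 12 pairs are complete.

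**Formulas (log scale).**
- Within-participant SD: σ = √ln(1 + CV²)
- Standard error of the fed minus fasted difference: SE = σ√(2/n)
- Success: estimate − t·SE_hat > ln(lower limit) and estimate + t·SE_hat < ln(upper limit), where t is the 1 − α quantile and α is the level of each one-sided test
- Power: the probability of success, integrated over the chi-square distribution of the variance estimate

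Results are given for 10 df (standard crossover with a period term) and 11 df (the model as written in 9.6.3.2.1, without one).

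**Numbers in.**
- CV 0.206: σ = √ln(1.042436) = 0.2039; SE = 0.2039 × √(2/12) = 0.0832
- CV 0.334: σ = √ln(1.111556) = 0.3252; SE = 0.3252 × √(2/12) = 0.1328

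**Power with 12 pairs, 10 df / 11 df.**

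| Scenario | 10% per side (80% CI) | 5% per side (90% CI) |
|---|---|---|
| CV 0.206, limits 0.80–1.25 | 80.1% / 80.5% | 60.6% / 61.5% |
| CV 0.334, limits 0.70–1.428 | 80.2% / 80.6% | 60.8% / 61.7% |

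The first column reproduces the plan's 80% in both scenarios. A simulation of 1,000,000 trials (10 df) gave 80.2% and 60.7% for the first row, and 80.3% and 60.8% for the second.

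**Is the reading right?** Solving for the CV that gives exactly 80% at 10% per side (10 df) returns 0.2062 and 0.3349; the protocol prints 0.206 and 0.334. Two scenarios with different limits both land on the stated values. At 5% per side, no alternative tried for CV 0.206 came within 2 points of 80%:
- normal approximation: 70.0%
- σ set equal to the CV: 59.2%
- unlogged scale: 58.3%
- parallel groups of 12: 65.9%
- parallel groups of 6: 17.7%
- CV read as that of the paired difference: 93.9 to 94.3%

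**What 12 pairs can support under the 90% CI rule.** Within 80 to 125%, power reaches 80% only at a CV of about 0.175 (10 df) or 0.176 (11 df) and below. At CV 0.206, 80% needs 16 complete pairs (80.5% / 80.9%). At CV 0.334, power within 80 to 125% is about 9%; 9.2 does not claim otherwise, because it pairs that CV with wider limits.

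**Fewer pairs (side note).** The note to Table 4 in section 1.3 says "Any participant who experiences vomiting at or between 0.25-3 h will be removed from statistical analysis of PK comparability between fasted/fed state". The replacement rule in 4.1.1.1 covers only "A participant requiring dose reduction or discontinuation from study before completion of at least 48 hours after dosing in fasted/fed state", so vomiting alone is not named as a ground for replacement. At CV 0.206 and 5% per side, 11 pairs give about 54 to 55% and 10 pairs about 46 to 47%. The documents give no vomiting rate.

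**The case against.** The strongest reply is that no sum is wrong: 9.2 says 10%, and at 10% per one-sided test both scenarios come to 80%. That is true, but it moves the fault without removing it. If 10% is per test, the figure describes a criterion the protocol does not use. If 10% was meant as the 90% CI, the figure should be about 61%. On either reading the two sections do not fit together.

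Next, the CV might be total. Power would then depend on the fed/fasted correlation: with 10 df at CV 0.206 and 5% per side, 61% at a correlation of 0, 78% at 0.25, 88% at 0.4 and 94% at 0.5. Reaching 80% needs about 0.26 to 0.28 in both scenarios. No document gives a correlation, and the within-participant reading recovers both printed CVs. It is still an inference, and the sponsor should confirm it.

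Last, little depends on the figure, and this stands. The number 12 is a guidance minimum and a floor, so extra enrolment could offset exclusions. The sub-study is optional and supports a secondary objective. Section 9.6.3.2.1 bases the clinical recommendation on the magnitude of the change and on exposure-response knowledge. SAP 2.1 has cancelled the food-effect analysis, so no reported result is affected. These facts limit the importance of the error; they do not make the stated power correct.

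**Conclusion.** The concern holds, as a minor error. The 80% in 9.2 is not the power of the criterion in 9.6.3.2.1. With 12 complete pairs, a true ratio of 1.0 and a within-participant CV of 0.206, power per parameter is about 61%, some 19 points below the stated figure. The chance of missing the criterion when there is no food effect is about 39% for one parameter (100 − 61), not 20%. The rule names both Cmax and AUC, so the chance that both pass is the same or lower.

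The scenario at CV 0.334 has the same fault, about 61% with its own limits and a 90% CI, and those limits are not part of the decision rule. The one assumption that matters is that the CV is within-participant. It fits both printed values closely, but the protocol does not state it.

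**What to change.** Confirm the definition of the CV, keep 12 as the guidance minimum, and replace the power sentence in 9.2 with wording such as:

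> With 12 complete pairs, a true fed/fasted ratio of 1.0 and the 90% CI required to lie within 80–125% (5% per one-sided test), power for each parameter is about 61% at a within-participant CV of 0.206 and reaches 80% only at a CV of about 0.175 or below. At a CV of 0.334 it is about 9%.

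Either delete the scenario with limits 0.70 to 1.428, or label it as a planning illustration outside the decision rule and give its 90% CI power of about 61%. If a total CV was meant, say so and state the assumed fed/fasted correlation.

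The cost is wording in one section and a less favourable power figure. The minimum number, the model and the decision rule do not change. If 80% per parameter at CV 0.206 is wanted, 16 complete pairs are needed, which the floor of twelve already permits.

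### The food-effect sizing claims 80% power at CV 0.334 only under limits of 0.70–1.428, but the sole success rule is a 90% CI within 80–125%, so that power figure does not describe the planned analysis

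*Protocol*

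**What the plan says.** Protocol section 9.2 states that for both Cmax and AUC "a total sample size of 12 patients achieves 80% power at a 10% significance level", on the condition that the true fed/fasted ratio is 1.0. Two scenarios follow. In the first the CV is 0.206 and "the equivalence limits of the mean ratio are 0.80 and 1.25". The second takes a CV of 0.334, and for that case the section says that "the equivalence limits of the mean ratio will be 0.70 and 1.428 to achieve the same level of power".

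Section 9.6.3.2.1 gives one decision rule, applied to Cmax and AUC: no food effect is concluded when the 90% CI of the fed/fasted ratio, "based on log-transformed data, is within the 80 to 125% equivalence limit". It contains no trigger based on the CV, no wider limits and no reference back to 0.70–1.428. Those limits appear nowhere else in the protocol or SAP. The same section also requires the fed/fasted ratios and their 90% CIs to be reported, and says the clinical importance of any food effect will be judged on its size and on the exposure–response relationship.

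Section 4.1.1.1 and Table 5 describe a randomised two-period crossover with six participants per sequence. Twelve is a minimum, which 9.2 also takes from FDA guidance. SAP section 2.1 states that the food-effect analysis will not be done, because enrolment was stopped.

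**The concern.** The sizing lets the equivalence limits depend on the variability, and the reason it gives is to hold power constant. The analysis section does not. A reader of 9.2 could believe that 12 participants give an 80% chance of concluding there is no food effect at a CV of 0.334. Under the rule that would be applied, the chance is far smaller.

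Section 4.2 says this cohort's data can be used to change dosing instructions in relation to food. It therefore matters that the criterion is fixed in one place before the CV is known, and that the stated power belongs to that criterion. If the two sections were reconciled only after the data were seen, the standard for declaring no food effect would depend on the data.

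**Working it through.** **Inputs.** From section 9.2: N = 12, power 80%, significance level 10% (sidedness not stated), true ratio 1.0, CV 0.206 with limits 0.80–1.25, CV 0.334 with limits 0.70–1.428. From section 9.6.3.2.1: 90% CI (5% per side), limits 0.80–1.25, fed status fixed and participant random. From section 4.1.1.1: 2×2 crossover, six per sequence. Assumption: the CV is within-participant. Power is per parameter.

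**Formulae.** Log-scale SD σ = √ln(1 + CV²). SE of the log ratio = σ√(2/12). Success requires the estimate ± t × estimated SE to lie inside the log limits. Power is exact, integrating over the distribution of the variance estimate. Error df is 10 if period and sequence are fitted and 11 for the written model; this shifts the crossover results below by at most about 1 percentage point. Df 10 is used unless stated.

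**Step 1: scale.** CV 0.206 gives σ = 0.204 and SE = 0.0832. CV 0.334 gives σ = 0.325 and SE = 0.1328.

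**Step 2: reproduce 9.2.** With 10% on each one-sided test (an 80% CI), power is 80.1% in the first scenario and 80.2% in the second. Both stated figures reproduce. They do not at 5% per side (60.6% and 60.8%), with the CV read as that of the paired difference (about 98% at 10% per side), or with a parallel design (about 41%). This supports the within-participant reading.

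**Step 3: change only the limits at CV 0.334.**

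| Level | Limits 0.70–1.428 | Limits 0.80–1.25 |
|---|---|---|
| 10% per side (reproduces 9.2) | 80.2% | 27.5% |
| 5% per side (written 90% CI) | 60.8% | 9.1% (8.9% with df 11) |

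Reading across a row gives the effect of the limits; reading down a column gives the effect of the confidence level. A simulation of 1,000,000 trials gave 9.2% for the bottom-right cell.

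**Step 4: why the last cell is so low.** At CV 0.334 and 5% per side, t = 1.812, so the CI half-width at the nominal SE is 1.812 × 0.1328 = 0.241. That exceeds ln 1.25 = 0.223. Even an observed ratio of exactly 1.00 passes only when the estimated SD comes out below its true value. The largest observed σ that can pass is ln(1.25) × √6 / t. With df 11 (t = 1.796) this is 0.304, a CV of 0.312; with df 10 it is 0.302, a CV of 0.309. Above an observed CV of about 0.31, the written rule cannot be met with 12 participants.

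**Step 5: written rule, N = 12, true ratio 1.0, over a range of CVs.**

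| CV | 0.15 | 0.20 | 0.206 | 0.25 | 0.30 | 0.334 |
|---|---|---|---|---|---|---|
| Power | 92% | 64% | 61% | 35% | 16% | 9% |

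Eighty per cent power holds only up to a CV of about 0.175. At CV 0.334, about 38 participants would be needed (80.3%; 36 give 77.3%).

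**The case against.** The strongest reply is that 9.2 is open about what it does. It ties the second 80% to the wider limits, so it already implies that 80–125% would not deliver 80% at CV 0.334. The two CVs also look solved for rather than expected: with N = 12, df 10 and 10% per side, the largest CVs giving 80% power are 0.2062 and 0.3349, which truncate to 0.206 and 0.334. On that view the sentence is a sensitivity statement about what 12 participants can resolve. This largely stands. A reader might infer that 9.2 expects a CV of 0.334, or promises 80% there under 80–125%; the text says neither. What does not stand is leaving the sentence as it is. It says the limits will be the wider pair, which reads as a rule, and it is not labelled as sensitivity.

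A reader might also infer that widening the limits could let a real food effect pass. If 0.70–1.428 were applied at CV 0.334 with a true ratio of 1.25, no food effect would be declared about 23% of the time with a 90% CI (37% at 10% per side), against at most 5% under the written rule. That would happen only if 9.2 overrode 9.6.3.2.1, and no analysis section authorises it.

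Three further points limit the weight. Twelve is a floor that also rests on the guidance minimum. The sub-study is optional and serves a secondary PK objective. The food recommendation does not rest on pass/fail alone. None of them makes the second power figure apply to the written rule.

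**Conclusion.** The inconsistency is real: the 80% stated at CV 0.334 does not apply to the planned analysis. Attributable to the limits alone, power falls from 80% to about 27% at the level that reproduces 9.2, or from about 61% to about 9% with the written 90% CI. It would be wrong to charge the whole distance from 80% to 9% to the limits, because part of it comes from sizing at 10% per side while the rule uses 5% per side. That is a separate mismatch, and it also affects the CV 0.206 scenario.

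The result assumes a within-participant CV, a true ratio of 1.0, exactly 12 participants and one parameter at a time. Requiring both Cmax and AUC to pass can only lower power; enrolling more than 12 would raise it. Since the documents give no expected CV, 9% is the power at one scenario in 9.2 and not a forecast. A reader might infer that this trial's results are affected; they are not, because the SAP drops the food-effect analysis. The defect is in the protocol's design statement.

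**What to change.** In section 9.2, state that a 90% CI within 80–125% is the only criterion for absence of a food effect, whatever the CV. Replace the two power figures with the power of that rule over a range of CVs, such as the Step 5 table, and note that with 12 participants it cannot be met above an observed CV of about 0.31. Either delete the 0.70–1.428 scenario or keep it labelled as a sensitivity statement that is not a decision rule.

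In section 9.6.3.2.1, add that the limits are not chosen from the observed CV. Add also that if the CI does not fall within 80–125%, the ratio and 90% CI already planned are reported without a conclusion that a food effect is absent.

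The cost is wording in two sections and no extra participants. The downside is a less favourable stated power.
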